### **2.5.2 Known Potential Benefits**

The proposed study is urgent. Currently there are no approved treatments for the patients intended for enrollment in SISTER who present within the 9-24 hour window. The alternative to participation in SISTER trial would be “no treatment” for these patients. Thus, SISTER participants stand to directly benefit from the potential of receiving a thrombus-dissolving medication that may be safe and may improve their chances of achieving a good outcome. Even though the EXTEND trial has shown potential benefit of rtPA treatment within the 4.5-9 h of stroke onset, in a patient population similar to the intended SISTER population, this practice is not yet widely adopted in the U.S. as there are several concerns regarding generalizability of EXTEND results. (Ma, Campbell et al. 2019, Ringleb, Bendszus et al. 2019) This practice is also not adopted in the US acute stroke clinical guidelines. (Powers, Rabinstein et al. 2019) Thus, patients who present within 4.5-9 who are not deemed eligible for rtPA by local investigators stand to benefit from participation in the study. For society, this study offers benefits including availability of a safe and effective acute treatment for patients who otherwise are untreated. In the long-term, this study has the potential for providing a safer and more effective alternative to plasminogen activator thrombolytics for all acute stroke patients, possibly obviating the need for procedural intervention in the large number of patients who don't have ready access to these procedures.

### **2.5.3 Assessment of Potential Risks and Benefits**

The proposed strategy for SISTER has gone through stages of review, critique, and revision from experts in the fields of stroke neurology, cardiology, and biostatistics. The inclusion and exclusion criteria are specifically chosen to only exclude conditions that may require special safety considerations for thrombolytics. The imaging selection component adds another layer of protection by ensuring that patients will only be enrolled that have significant salvageable brain tissue, and minimal amount of irreversible injured tissue (which is most likely to cause intracranial bleeding). The Multiple Principal Investigators team (MPIs), Independent Medical Monitor, and DSMB will closely and comprehensively monitor pre-specified safety events, AEs, SAEs and unanticipated problems (UPs), according to plans outlined in the Data and Safety Monitoring Plan attachment. They will be reported to the IRB and the sponsor as outlined in the protocol, who may suggest study modifications as appropriate to protect human participants. After the study drug infusion, patients will be monitored for immediate infusion reactions in a high acuity hospital setting for prompt identification and treatment.

---

Further, the study drug will be shipped and maintained under strict conditions according to our FDA-approved IND. We will strictly adhere to the study protocol, collect high-quality data, and thoroughly train and, periodically retrain, all research and clinical personnel involved with the study regarding the details of study protocol and procedures. During the study period, all patients will receive care according to the local and most recent acute stroke guidelines. Study personnel will be readily available to answer questions at any time during the study course. The small risk for violation of confidentiality will be minimized by training all study personnel with the web-based Responsible Conduct of Research Training Program.

Inventing a safer and more effective alternative to the current paradigm of thrombolytic, i.e., plasminogen activators, addresses an urgent gap in the acute stroke treatment that needs to be filled. SISTER trial will test a new paradigm in acute stroke thrombolytic therapy using a monoclonal antibody against a2-antiplasmin. If successful, this trial will provide important insights into safety and preliminary efficacy of this new molecule for the treatment of acute ischemic stroke patients, which will be immediately translated into a phase 2/3 pivotal trial. The findings of SISTER trial will also be relevant to the broader acute ischemic stroke population including those presenting within the earlier time window and harboring a large cerebral blood vessel occlusion.

### **3 OBJECTIVES AND ENDPOINTS**

#### **3.1 Primary Objective**

To identify a dose of TS23 that is safe and potentially more efficacious than placebo for the treatment of patients from 4.5 to 24 hours of ischemic stroke onset, who have evidence of core-penumbra mismatch on perfusion imaging.

#### **3.2 Endpoints**

##### **Primary Endpoints:**

1. Safety: ANY ICH visualized on the CT scan obtained 30 ( $\pm$ 44) hours after study drug administration.
2. Efficacy: National Institutes of Health (NIH) Stroke Scale Score at 30 ( $\pm$ 4) h after study drug administration (adjusted for the baseline NIHSS in analysis)

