**Endpoints:**

**Primary Endpoints:**

1. Safety: ANY intracranial hemorrhage (ICH) visualized on the CT scan 30 ( $\pm 4$ ) h after study drug administration.
2. Efficacy: NIH Stroke Scale Score at 30 ( $\pm 4$ ) h after study drug administration (adjusted for the baseline in analysis)

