## 7.3 Lost to Follow-Up

When scheduling follow-up visits, multiple attempts should be made in order to reach the participant. If the participant cannot be reached, multiple attempts should be made to the person(s) listed as secondary contact. If no contact is made after multiple attempts, alternative methods should be considered in order to obtain contact with the participant and/or verify their living status. Examples of alternative methods of contact are fax, other scheduled medical appointments, and certified letter.

**Efforts should be made for up to 150 days from randomization to determine the participants' 90-day status.** A participant may be considered lost to follow-up if they cannot be reached for up to 150 days from randomization, despite following the procedures outlined above. The following are considered to be reasons a subject is lost to follow-up: unable to contact for follow-up, moved away from and unable to return for follow-up visits. Appropriate documentation of lost to follow-up will be maintained in the subject's research record at the site.

All effort is put forth to ensure complete follow-up for all participants that had study drug initiated, in particular with the assessment of the primary outcome at 24-30 hr. This is expected to be extremely rare for patients enrolled in SISTER given that majority of the patients will be admitted to the hospital at least for the duration of 24-30 hours following their acute stroke. The study personnel will note the patient's name, date-of birth, and medical record numbers upon enrollment. They will also clearly communicate and remind the clinical care teams about the study assessment timeline to from time-to-time. Other measures taken to minimize loss to follow-up will be outlined in site-specific SOPs. It is possible that a small fraction of patients may die before completing the 30 ( $\pm 4$ ) hour assessments. Our plan to account for such missing data is outlined in the statistical analysis plan (SAP).

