## 9 SAFETY ASSESSMENTS

### 9.1 Primary safety endpoint

ANY ICH visualized on the 30 ( $\pm 4$ ) h CT scan is the primary study endpoint for SISTER. This will be determined on the 30 ( $\pm 4$ ) h CT scan uploaded in the central imaging databank by local study personnel, by a trained neuroradiologist who is blinded to the participant's study group assignment.

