### 10.2 Primary Analysis

The primary analysis will be Bayesian. We will test whether the best dose of TS23 has at least 25% Utility ("Promising Zone"). The trial is a success if the best dose has utility of 0.25 or higher with at least 80% probability. Such a utility can be achieved through various combinations of 24-hour NIHSS improvement and ICH rate.

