#### 10.2.2 Utility Function

We define a utility function based the combination of the primary safety outcome,  $U_1$ , and the primary efficacy outcome,  $U_2$ , as  $U_1 \times U_2$  where 1 is perfect utility and zero is no utility. This utility score

---

provides an integrated assessment of safety (any radiographic ICH on follow-up CT) and preliminary efficacy (improvement in 24-hour NIHSS) and is used to define our “promising zone”.

For the safety outcome (ICH),  $U_1=1$  if the ICH response rate for that dose is  $\leq 40\%$  and  $U_1=0$  if the ICH rate is 70% or greater and takes a quadratic function between 40%-70%. This was based on a clinical discussion of what would be an acceptable rate of any ICH.

For the primary efficacy outcome (NIHSS), the utility equal

is defined based on the mean difference from control adjusted for baseline NIHSS.  $U_2=1$  if the dose is 2 points better than control and  $U_2=0$  if it is no different from control with a quadratic function in between 0 and 1.

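### The primary ICH window is misprinted as 30 (±44) h in section 3.2, and a 24 h time that does not match the 30 (±4) h endpoint remains in 7.3, 10.2, 10.2.2, Table 3 and the death rule of 10.5

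*Protocol*

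**What the plan says.** Section 3.2 lists two primary endpoints, one under the other, with different windows. The safety endpoint is "ANY ICH visualized on the CT scan obtained 30 ( $\pm$ 44) hours after study drug administration". The efficacy endpoint is the NIH "Stroke Scale Score at 30 ( $\pm$ 4) h after study drug administration (adjusted for the baseline NIHSS in analysis").

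Elsewhere the safety endpoint has the narrow window. The synopsis has "ANY intracranial hemorrhage (ICH) visualized on the CT scan 30 ( $\pm 4$ ) h after study drug administration", and section 9.1 has "ANY ICH visualized on the 30 ( $\pm 4$ ) h CT scan is the primary study endpoint for SISTER". Section 8.4 and the schedule of activities place the only post-dose CT at the 30 (±4) h visit.

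For the efficacy variable, section 10.2 says "Such a utility can be achieved through various combinations of 24-hour NIHSS improvement and ICH rate", and the introduction to the utility in 10.2.2 refers to "preliminary efficacy (improvement in 24-hour NIHSS"). The column heading of Table 3 also gives the simulated NIHSS as a 24-hour value. Section 10.9, by contrast, tabulates the NIHSS at 30 (±4) h.

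Section 7.3 asks for complete follow-up, "in particular with the assessment of the primary outcome at 24-30 hr", and a few sentences later speaks of the 30 (±4) h assessments.

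Section 10.5 assigns the worst observed NIHSS and an ICH event to a patient who dies a neurological death before 24 hours. The synopsis entry for symptomatic ICH, a secondary endpoint, opens with 30 (±6) h; its own bracketed definition and sections 3.2 and 9.2 use 30 (±4) h.

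**The concern.** Any ICH and the early NIHSS are the only two inputs to the utility U1 × U2. The utility drives the response-adaptive allocation and the Go rule, and the ICH rate also drives the safety stopping quantity. Each endpoint should therefore have one time, stated identically wherever it appears.

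As written, new blood on an unscheduled CT at 60 h is a primary event under 3.2 and is not one under 9.1. The section that fixes the success criterion names an NIHSS time outside the visit that collects it. Section 10.5 is the one place where the 24 h figure acts as a rule and not only as a label: it decides which early deaths receive the unfavourable value.

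**Working it through.** The protocol gives no figure to reproduce here. The check is interval arithmetic on each stated window against the scheduled visit.

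| Place | Stated time | Interval after dosing |
|---|---|---|
| Synopsis, 8.4, 9.1 (ICH on CT) | 30 (±4) h | 26 to 34 h |
| 3.2 (ICH on CT) | 30 (±44) h | upper limit 74 h |
| Synopsis, 3.2, 3.3, 8.4, 10.9 (NIHSS) | 30 (±4) h | 26 to 34 h |
| 10.2, 10.2.2, Table 3 (NIHSS) | 24 h | 24 h |
| 7.3 (primary outcome) | 24 to 30 h | 24 to 30 h |
| 10.5 (death rule) | before 24 h | 0 to 24 h |
| 8.5 (next NIHSS) | 72 (±12) h, or discharge if sooner | 60 to 84 h |
| Synopsis (symptomatic ICH) | 30 (±6) h | 24 to 36 h |

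**Section 3.2.** The upper limit is 30 + 44 = 74 h, against 30 + 4 = 34 h, an excess of 74 − 34 = 40 h. The nominal lower limit is 30 − 44 = −14 h, but the sentence requires the scan to follow dosing, so the negative part has no meaning. The schedule contains no CT between 34 and 74 h, so only an unscheduled scan could fall there.

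**24-hour NIHSS.** 24 < 26, so 24 h lies outside the 30 (±4) h visit. The NIHSS is scheduled at baseline, 30 (±4) h, 72 (±12) h or discharge if sooner, day 30 and day 90. No visit is fixed at 24 h.

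**Section 7.3.** The intervals 24 to 30 h and 26 to 34 h share 26 to 30 h: 4 of the 6 hours that 7.3 names, and 4 of the 8 hours of the visit.

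**Section 10.5.** The worst-value rule ends at 24 h and the assessment takes place at 26 to 34 h. The uncovered gap is 26 − 24 = 2 h at the shortest and 34 − 24 = 10 h at the longest. A neurological death in that gap leaves the NIHSS missing for the same reason that 10.5 itself treats as potentially informative, yet the rule does not reach it.

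**Synopsis, symptomatic ICH.** 30 (±6) h is 24 to 36 h, which is 12 h wide; 30 (±4) h is 8 h wide.

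**Table 3.** The simulated values (placebo mean 7, SD 5.5) come from adaptive-trial simulations whose priors the protocol leaves to the SAP, so they were not reproduced. Correcting a time label does not alter them.

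**The case against.** The strongest reply is that this is proofreading. The ±44 is evidently a doubled digit: the next line of 3.2, the synopsis, the schedule, 8.4 and 9.1 all say ±4, and 9.1 gives the working rule, a central blinded reading of the 30 (±4) h CT. The sentences in 10.2.2 that define U2 do not mention 24 hours; they refer to the primary efficacy outcome, which is defined at 30 (±4) h. Section 7.3 concerns retention and does not set visit times. All of this stands, and it limits the weight of the point.

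It also rules out three stronger readings that a reader might infer:

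- **Pre-dose scans would count as primary events.** The wording of 3.2 requires a scan obtained after dosing, so blood on the qualifying scan is excluded even on the literal text.
- **The utility rests on a value that is never measured.** U2 is tied to the primary efficacy outcome, and the 30 (±4) h visit collects it. The 24-hour wording is a wrong label on an identifiable variable.
- **A definite share of assessments would miss the window because of 7.3.** That would need a distribution of assessment times, which the protocol does not give, and sites take visit timing from 8.4 and the schedule.

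The reply does not dispose of 10.5, where the 24 h is a cut-off and no other protocol passage supplies a different one. Section 7.3 says that the SAP covers deaths before the 30 (±4) h assessment. The SAP is not at hand and may close the gap, but the protocol's own rule would still stop at the wrong time.

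**Conclusion.** The inconsistency is real and lies in the current text of a primary endpoint definition and of the success-criterion section. Its practical size is small. The intended window, 26 to 34 h, is clear from most of the document, and the literal 74 h limit matters only for unscheduled CTs. The one substantive consequence is in 10.5: neurological deaths between 24 h and the assessment, a gap of 2 to 10 h, fall outside the worst-value rule. The protocol gives no figure for how many such deaths to expect; 7.3 expects only a small fraction to die before the assessment.

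No stated power or type I error figure changes. The conclusion assumes that 30 (±4) h is the intended time for both primary endpoints, as the synopsis, 3.3, 8.4, 9.1 and 10.9 indicate. It should be corrected at the next amendment.

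**What to change.** - **3.2:** change ±44 to ±4.
- **7.3, 10.2, 10.2.2:** give the primary outcome time as 30 (±4) h.
- **10.5:** replace the 24 h death cut-off with one tied to the 30 (±4) h assessment, so that every neurological death before that assessment is covered, and check that the SAP says the same.
- **Synopsis, symptomatic ICH:** change ±6 to ±4, as in 3.2 and 9.2.
- **Table 3:** if the mean of 7 and SD of 5.5 describe the NIHSS at 30 (±4) h, relabel the column. If they are 24-hour figures, keep the label and state that they stand in for the 30 h endpoint. Relabelling without checking could misdescribe what was simulated.

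A global replacement of 24 h would be wrong, since the figure also appears in the symptomatic ICH definition and in the antithrombotic restriction for other reasons. The cost is wording in the next amendment, with no new visit, scan or simulation.

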##### **Secondary Endpoints:**

##### **Clinical Efficacy (In hierarchical order):**

1. Improvement in level of global disability (mRS distribution) at 90 ( $\pm$ 7) days.
2. Frequency of excellent functional outcome (mRS 0-1) at 90 ( $\pm$ 7) days.
3. NIHSS at 72 ( $\pm$ 12) h (or discharge if sooner; adjusted for the baseline in analysis)

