**Clinical Efficacy:**

1. Improvement in level of global disability (Modified Rankin Scale (mRS) distribution) at 90 ( $\pm 7$ ) days.
  2. Frequency of excellent functional outcome (mRS 0-1) at 90 ( $\pm 7$ ) days.
  3. National Institutes of Health Stroke Scale (NIHSS) at 72 ( $\pm 12$ ) h (or discharge if sooner; adjusted for the baseline in analysis)
-

Pharmacokinetics and anti-drug antibodies:

1. Pharmacokinetic (PK) profile of TS23 at 3 (+/-1) h and 30 ( $\pm$ 4) h after completion of therapy and 90 ( $\pm$ 7) days.
2. Evaluation of anti-drug antibodies to TS23 (at baseline and 90 ( $\pm$ 7) d follow-up visit).

Safety:

1. Incidence of symptomatic ICH within 30 ( $\pm$ 6) h of study drug administration [SITS-MOST definition (a local or remote type II parenchymal hemorrhage within 30 ( $\pm$ 4) h after treatment associated with a  $\geq$  4-point deterioration on the NIHSS score from baseline or from the lowest score from baseline to 24 hours, or leading to death.)]
2. Incidence of non-ICH major or clinically relevant non-major bleeding within 30 days of study drug administration.
3. Non-bleeding, serious adverse events (SAEs) within 90 ( $\pm$ 7) days
4. Incidence of stroke-related and all-cause deaths within 90 ( $\pm$ 7) days
5. Plasma fibrinogen levels at 3 (+/-1) h after completion of study drug administration

**Study Population:** We will enroll a total of 300 adults ( $\geq$ 18 years) with acute ischemic stroke who have a baseline NIHSS  $\geq$ 6 and are able to receive study drug within 4.5-24 hours after stroke onset (or last known well) who have evidence of core-penumbra mismatch on baseline perfusion imaging and are not planned for endovascular intervention or standard of care intravenous (IV) thrombolysis.

**Phase:** 2

**Description of Sites/Facilities Enrolling Participants:** Consecutive eligible patients will be screened and enrolled in up to 50 comprehensive stroke centers in the U.S. Currently, no sites outside of the U.S. are planned.

**Description of Study Intervention:** The study intervention arms are TS23 (dosed at 3, 5, 7, or 10 mg/kg) or matching placebo. Study drug is administered intravenously as

[figure not shown]

short IV infusion after reconstitution over ~15 minutes (max dose of 1000 mg).

**Study Duration:** 54 months

**Participant Duration:** 3 months

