### **3.3 Rationale and assessment of endpoints**

**NIHSS:** We choose 30 ( $\pm 4$ ) h NIHSS (adjusted by baseline NIHSS) as our primary efficacy outcome measure as an ideal combination of good surrogate properties, feasibility, and strong biological rationale. NIHSS is a common surrogate marker for early-phase stroke trials ([Lyden, Lu et al. 2001](#), [Saver, Goyal et al. 2015](#), [Lapergue, Blanc et al. 2017](#), [Goldstein, Lennihan et al. 2018](#)) and, when analyzed appropriately using regression methods, ([Young, Weir et al. 2005](#), [Meyer, Broocks et al. 2020](#), [Mistry, Yeatts et al. 2020](#), [Mistry, Yeatts et al. 2021](#)) is strongly associated with patient-centered outcomes, including the 90d mRS global disability scale. A 72-hour NIHSS will be measured as a key secondary outcome to capture the prolonged neurological effects of TS23 in the subacute period. To minimize bias, the NIHSS will be assessed by a certified rater who will be blinded to the patients' study group assignment.

**Any ICH:** We choose ANY ICH to evaluate the safety of TS23 more robustly, as opposed to the commonly used symptomatic ICH outcome. In recent studies, ANY ICH is shown to be associated with worse 90-day global disability outcomes. ([Gay, Collie et al.](#)) In fact, we account for this safety outcome in our sample size and power calculations and are well-positioned to readily detect safety

---

issues with TS23. EXTEND trial data in the non-LVO subset (personal communication, [name]) and data pooled from other major thrombolytic trials (Lees, Bluhmki et al. 2010) informed our assumptions.

**mRS** analyzed as ordinal global disability scale and dichotomous excellent outcome (mRS 0-1): mRS is the most commonly used, patient-reported, functional disability outcome in acute stroke trials. (Lees, Bath et al. 2012, Lees, Khatri et al. 2016) To increase outcome comparability and minimize bias, the modified Rankin Scale assessments of global disability will be obtained at all sites using the formal, algorithmic Rankin Focused Assessment-Ambulatory (RFA-A) method by trained raters. (Saver, Filip et al. 2010)

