## **5.2 Exclusion Criteria**

1. Plan to receive endovascular treatment.
  2. Received or plan to receive IV thrombolysis.
  3. Pre-stroke modified Rankin score >2.
  4. Previous treatment with TS23 or known previous allergy to antibody therapy.
  5. Known pregnancy, women who are breastfeeding or plan to breastfeed within 3 months of receiving TS23 or have a positive urine or serum pregnancy test for women of childbearing potential.
  6. Known previous stroke in the past 90 days.
  7. Known previous intracranial hemorrhage, intracranial neoplasm, subarachnoid hemorrhage, or arterial venous malformation.
  8. Known active diagnosis of intracranial neoplasm.
  9. Clinical presentation suggestive of a subarachnoid hemorrhage, even if initial CT scan was normal.
  10. Surgery or biopsy of parenchymal organ in the past 30 days.
  11. Known trauma with internal injuries or persistent ulcerative wounds in the past 30 days.
  12. Severe head trauma in the past 90 days.
  13. Persistent systolic blood pressure >180mmHg or diastolic blood pressure >105mmHg despite best medical management.
  14. Serious systemic hemorrhage in the past 30 days.
  15. Known hereditary or acquired hemorrhagic diathesis, coagulation factor deficiency, or oral anticoagulant therapy with International Normalized Ratio (INR) >1.7.
-

16. Platelets <100,000/mm^3.
17. Hematocrit <25 %.
18. Elevated aPTT above laboratory upper limit of normal.
19. Creatinine > 4 mg/dl, or patients receiving renal dialysis, regardless of creatinine.
20. Received heparin or low molecular weight heparins (such as Dalteparin, Enoxaparin, Tinzaparin) in full therapeutic dose within the previous 24 hours.
21. Received Factor Xa inhibitors (such as Fondaparinaux, apixaban or rivaroxaban) within the past 48 hours.
22. Received direct thrombin inhibitors (e.g., argatroban, dabigatran, bivalirudin, desirudin, lepirudin) within 48 hours.
23. Received glycoprotein IIb/IIIa inhibitors within the past 14 days.
24. Known pre-existing neurological or psychiatric disease, which would confound the neurological/functional evaluations.
25. Current participation in another research drug treatment protocol (i.e., participants could not start another experimental agent until after 90 days).
26. Concurrent acute myocardial infarction, pulmonary embolism, deep venous thrombosis, or other thrombotic event that requires anticoagulation or anti-platelet treatment.

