## 8.1 Baseline

Patients presenting with acute ischemic stroke will be evaluated by a stroke team physician, in accordance with institutional practice, to establish study eligibility. All consecutive patients meeting study entry criteria will be enrolled in the trial.

Participants enrolled in SISTER should not receive antithrombotics for at least 24 hours after study drug administration.

The study order sets will specifically include an order not to administer antithrombotics within the first 24 hours after study drug administration. This will also be closely monitored as participants will be admitted to the intensive care unit setting for at least first 24 hours after drug admission.

The following data will be documented at the baseline evaluation for randomized patients:

- Demographics: Age, sex, race/ethnicity
  - Medical history regarding presence of concomitant medical conditions (e.g. hypertension, diabetes, hyperlipidemia, atrial fibrillation, prior ischemic stroke, prior hemorrhagic stroke, current or past smoking)
  - Vital signs: Systolic and diastolic arterial blood pressure; heart rate, temperature
  - Concomitant medications at time of stroke onset (anticoagulation, antiplatelets, antihypertensives, statins, antidiabetics, cholesterol reducers)
  - Pre-stroke functional state: pre-stroke modified Rankin Scale, pre-stroke ambulatory status (independent, with assistance, unable)
  - Laboratory Evaluation
    - Measurement within 12 hours prior to study drug administration (if there are multiple measurements, then consider the latest measurement)
      - SOC: aPTT, PT with INR, CBC, platelet count.
    - First measurements upon presentation to study hospital, within 2-3 hours of study drug administration):
      - SOC: Glucose, creatinine
    - First value collected during hospitalization:
      - SOC: Hemoglobin A1C, Lipid Panel containing total cholesterol, HDL, LDL & triglyceride.
  - Neurologic Deficit: NIHSS upon arrival to the study hospital
-

- Brain and Vascular imaging at presentation:
    - CT or MRI
    - CTA or MR angiography (MRA)
    - CTP or MRI-PWI, if applicable per institutional practices
  - Initial Workflow Time Metrics: Date and time of:
    - Last known well (LKW)
    - Symptoms first observed (SFO)
    - Outside hospital (OSH) date/times (if patient first presented to an OSH):
      - Arrival at OSH (“Door-In”)
      - Departure from OSH (“Door-Out”)
    - Study Hospital date/times:
      - Arrival at Study Hospital

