## **10.8 Analysis of the Secondary Endpoints**

Secondary analyses will compare all doses to control by graphing the raw and model-fitted means and 95% CI. Group means (adjusted for baseline NIHSS and age) will be plotted with 95% confidence intervals around the mean for each dose and control. No formal hypothesis testing will be performed and no p-values reported for secondary efficacy outcomes.

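### Patients with pre-stroke mRS 2 are eligible but can hardly reach the mRS 0-1 endpoint, and pre-stroke mRS is not among the stated covariates for the secondary analyses

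*Protocol*

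**What the plan says.** **Eligibility.** Protocol section 5.2, exclusion 3, reads "Pre-stroke modified Rankin score >2". Pre-stroke mRS 0, 1 and 2 are therefore all eligible.

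**Endpoint.** Section 3.2 puts two 90-day mRS endpoints first and second in its clinical efficacy order:
- first, "Improvement in level of global disability (mRS distribution) at 90 ( $\pm$ 7) days";
- second, "Frequency of excellent functional outcome (mRS 0-1) at 90 ( $\pm$ 7) days".

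The synopsis (1.1) gives the same cut, and section 3.3 describes the mRS as "analyzed as ordinal global disability scale and dichotomous excellent outcome (mRS 0-1"). None of the three places makes any allowance for the pre-stroke level.

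**Data.** Section 8.1 records "Pre-stroke functional state: pre-stroke modified Rankin Scale, pre-stroke ambulatory status", and the Schedule of Activities lists pre-stroke mRS as a research procedure at baseline.

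**Analysis.** Section 10.8 states "Group means (adjusted for baseline NIHSS and age) will be plotted with 95% confidence intervals". Pre-stroke mRS is not named there. The same section says that secondary efficacy outcomes get no formal test and no p-value.

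**The concern.** A fixed cut at mRS 0-1 treats two different courses alike. A patient who was at 2 before the stroke and is at 2 on day 90 has lost nothing. A patient who was at 0 and is at 2 has new lasting disability. Both are recorded as not excellent. Unless they improve beyond their pre-stroke state, patients who enter at mRS 2 cannot respond on any arm.

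Two things follow for the reading of this endpoint. The responder rate has a ceiling below 100% in every arm, which shrinks the difference between a dose and placebo. In addition, a strong predictor of both 90-day mRS endpoints is collected but left out of the stated adjustment, so chance differences between arms in the pre-stroke score stay in the estimates. These results will be read as arm estimates without a test, so what each arm's figure means matters to the reader.

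**Working it through.** The protocol states no rate, effect size or power for mRS 0-1. The simulations in Table 3 concern NIHSS and any ICH only. There is thus no figure of the plan to reproduce, and the sizes below are illustrations.

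**Inputs from the protocol**
- Eligible pre-stroke mRS: 0, 1, 2 (5.2).
- Responder: mRS 0-1 at day 90 (1.1, 3.2, 3.3).
- Total 300. Control has 10 in the burn-in and 13 in each later block of 50 (4.1): 10 + 5 × 13 = 75. That leaves 225 on active drug over four doses, about 56 per dose on average.

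**Assumptions (not in the protocol)**
- Share q with pre-stroke mRS 2: 5-20%.
- No patient with pre-stroke mRS 2 ends at 0-1.
- Rates among the other patients: 30% against 40%.
- For chance imbalance: 50 patients in each of two arms, and q = 10%.

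**Step 1. Classification**

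| Pre-stroke mRS | Day-90 mRS | Course | Scored as |
|---|---|---|---|
| 0 | 1 | slight change | responder |
| 2 | 2 | full return to prior state | non-responder |
| 0 | 2 | new disability | non-responder |

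**Step 2. Ceiling and dilution.** Each arm rate is (1 − q) × the rate among the others, so the difference is (1 − q) × 10 points.

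| q | Patients of 300 | Ceiling | Rates | Difference |
|---|---|---|---|---|
| 5% | 15 | 95% | 28.5% v 38.0% | 9.5 |
| 10% | 30 | 90% | 27.0% v 36.0% | 9.0 |
| 15% | 45 | 85% | 25.5% v 34.0% | 8.5 |
| 20% | 60 | 80% | 24.0% v 32.0% | 8.0 |

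**Step 3. Chance imbalance in q**
- SD of the share in one arm: √(0.10 × 0.90 / 50) = 4.2 points.
- SD of the difference in share between two arms: √2 × 4.2 = 6.0 points.
- Effect on the difference in responder rates: 6.0 × 0.30 = 1.8 to 6.0 × 0.40 = 2.4 points, so about 2 points.

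**Step 4. Set against ordinary sampling error.** Take 35% among the others, which gives 0.90 × 35% = 31.5% overall. The SD of a two-arm difference is √(2 × 0.315 × 0.685 / 50) = 9.3 points. The imbalance part is 6.0 × 0.35 = 2.1 points and is already inside the 9.3, since (2.1 / 9.3)² is about 5% of the variance. Adjustment for pre-stroke mRS can remove roughly that part.

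**The case against.** The strongest case is that nothing here is an error. An eligibility limit of 2 and an absolute threshold of 0-1 can stand side by side. The endpoint is named for an excellent outcome, not for return to the pre-stroke state. Mild prior disability and a strict cut are compatible choices, and counting return to mRS 2 as success targets a different quantity. This stands. The documents do not support the reading that strict mRS 0-1 is wrong and must be replaced as the headline definition.

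The point is also partly covered elsewhere. The ordinal mRS distribution ranks first, does not depend on the 0-1 cut, and still credits a patient who ends at 2 rather than 3 to 6. Exclusion 24 removes known neurological or psychiatric disease that would confound the functional evaluation, so the assumed share may be too high. Section 6.3.1 promises balance on known prognostic variables without listing them, so pre-stroke mRS is shown neither as balanced nor as omitted. All of this keeps the matter small. Even with perfect balance, the ceiling and the shared scoring of the two courses would remain.

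Finally, covariates can be left to the SAP. The SAP could add this one. But section 10.8 does state a list, baseline NIHSS and age, and that list omits a score the trial collects.

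Three stronger inferences are tempting and fail:
- That the dose ranking of the trial could shift. Utility is built from any ICH and NIHSS alone (10.2.2). The target dose, the adaptive allocation and the Go rule all use utility (10.2.3.1, 4.1, 10.2.4).
- That chance imbalance moves the responder rates by 6 points. That figure is the SD of the difference in the share with pre-stroke mRS 2. The effect on the rates is about 2 points, and it is not an error on top of ordinary sampling variation.
- That the excellent-outcome rate is understated by some points. This is so only after return to mRS 2 has been redefined as excellent, and it would apply to every arm.

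**Conclusion.** The concern holds as a minor one. A patient with pre-stroke mRS 2 who fully recovers is a non-responder on the second-ranked clinical efficacy endpoint, and pre-stroke mRS is absent from the covariates stated for the secondary analyses.

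Under an assumed 5-20% share with pre-stroke mRS 2, the attainable rate is about 95-80%, and a 10-point difference among the others is seen as about 9.5-8.0 points. At an assumed 10% share and 50 per arm, chance imbalance accounts for an SD of about 2 points in a two-arm difference at response rates of 30-40%. That is part of the usual sampling error, and adjustment can reduce it. The share, the response rates and the arm size of 50 are assumptions. The dilution also assumes that no patient improves beyond pre-stroke mRS 2.

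Only the descriptive 90-day mRS results are touched. The primary analysis and the sample size of 300 are not affected.

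**What to change.** 1. In section 10.8, add pre-stroke mRS to baseline NIHSS and age as a covariate for both 90-day mRS endpoints. For the binary endpoint it is safer to enter it as a numeric score: with few or no responders at pre-stroke mRS 2, a separate category may have no stable estimate.
2. Keep strict mRS 0-1 as the stated endpoint. Beside it, prespecify a supportive analysis that counts as excellent a day-90 mRS of 0-1, or return to the pre-stroke mRS if that was 2.

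The cost is one additional descriptive analysis and a few words in 10.8. The data are already collected, so no visits, patients or forms are added. Keeping the strict cut preserves comparability with trials that use it. Both changes should be fixed before unblinding.
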